6.1.3. Analysis Methods

6.1.3.1. Double-Blind Treatment Period (Period 2): Main Protocol

The primary analysis method for categorical data for treatment group comparisons will be Fisher's exact test. The difference of the proportions and the 95% CI of the difference will be included.

Secondary analyses for the primary efficacy measures, PASI 75 and sPGA(0,1), and other categorical efficacy and health outcome measures, will be conducted using a logistic regression analysis with treatment group, region, baseline sPGA score (severity of Ps), and baseline weight category (<25 kg, ≥25 to ≤50 kg, or >50 kg) as factors. The odds ratio and the corresponding 95% CI will be reported.

The analyses for the continuous efficacy and health-outcome variables will be made using analysis of covariance (ANCOVA) and mixed model for repeated measures (MMRM) analysis. The ANCOVA model includes treatment group, region, baseline sPGA score, baseline weight category, and baseline value. Type III sums of squares for the least-squares means will be used for the statistical comparison; the 95% CI will be reported.

When the MMRM is used, the model will include treatment, region, baseline sPGA score, baseline weight category, baseline value, visit, treatment-by-visit, and baseline-by-visit interactions as fixed factors. The covariance structure to model the within-subject errors will be unstructured. The Kenward-Roger method will be used to estimate the denominator degrees of freedom. Type III tests for the least-squares means will be used for the statistical comparison; the 95% CI will be reported. Treatment comparisons at Week 12 and all other postbaseline visits will be reported.

If the unstructured covariance matrix results in a lack of convergence, the heterogeneous Toeplitz covariance structure, followed by the heterogeneous autoregressive covariance structure, followed by the compound symmetry will be used. This order is specified according to a decreasing number of covariance parameters in the structure. The sandwich estimator (Diggle et al. 1994) for the covariance estimation will be used by specifying the EMPIRICAL option in SAS PROC MIXED. When sandwich estimation is used, the Kenward-Roger approximation for denominator degrees of freedom cannot be used. Instead, the DDFM= BETWITHIN option will be used to estimate denominator degrees of freedom.

Fisher's exact test will be used for all adverse events (AEs), baseline characteristics, discontinuation, and other categorical safety data. The continuous baseline characteristics will be analyzed using an analysis of variance (ANOVA) model with treatment as a factor. Continuous vital sign data and laboratory values will be analyzed by an ANCOVA with treatment and baseline value in the model.

6.1.3.2. Double-Blind Treatment Period (Period 2): Protocol Addendum(2)

The analysis method for categorical data for treatment group comparisons will be Fisher's exact test. The difference of the proportions and the 95% CI of the difference will be included.

Fisher's exact test will be used for all AEs, baseline characteristics, discontinuation, and other categorical safety data. The continuous baseline characteristics will be analyzed using an ANOVA model with treatment as a factor. Continuous vital sign data and laboratory values will be analyzed by an ANCOVA with treatment and baseline value in the model.

6.1.3.3. Combined Treatment Periods

Data for the combined treatment periods will be summarized using descriptive statistics.

6.1.3.4. Double-Blind Randomized Withdrawal Period (Period 4)

The time to relapse (loss of response; sPGA ≥ 2) during Double-Blind, Randomized Withdrawal Period (Period 4) is defined as:

Time to relapse (days)

$$= \text{date of first sPGA} \geq 2 \text{ during Period 4} - \text{date of Week 60 rerandomization} + 1$$

If a patient has not experienced relapse by completion or early discontinuation of Period 4, the patient will be censored at the date of his/her last visit during Period 4.

The number of patients at risk and experiencing a relapse event by each scheduled visit during Period 4 will be presented by treatment group. The Kaplan-Meier estimate of the proportion of patients relapsing will be presented for each visit. Treatment group comparisons will be performed using the log-rank test. For each treatment group, a Kaplan-Meier plot of the time to relapse will be provided.

The analysis method for categorical data for treatment group comparisons will be Fisher's exact test. The difference of the proportions and the 95% CI of the difference will be included.

Fisher's exact test will be used for all AEs, baseline characteristics, discontinuation, and other categorical safety data. The continuous baseline characteristics will be analyzed using an ANOVA model with treatment as a factor. Continuous vital sign data and laboratory values will be analyzed by an ANCOVA with treatment and baseline value in the model.

6.2. Adjustments for Covariates

Clinical Protocol RHCD (main study), the randomization at the beginning of the Double-Blind Treatment Period (Period 2) is stratified by geographic region. With the exception of the primary analysis (that is, Fisher's exact test), efficacy and health-outcome analyses during Period 2 will include geographic region and baseline weight category in the analysis models.

In general, when an MMRM is to be used for analyses, baseline value and baseline-by-visit interactions will be included as covariates; when an ANCOVA is to be used for analyses, baseline value will be included as a covariate.

Protocol Addendum RHCD(2), for the double-blind randomized withdrawal period (Period 4), subjects were re-randomized to ixekizumab according to their weight at the time of re-randomization. The stratification factor, weight at the time of re-randomization, will not be included in the analysis models.

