- a Randomization will be stratified by region (United States/Canada, EU countries, and rest of the world) and by etanercept approval status: 1) Subjects with severe pediatric Ps (PASI ≥ 20 or sPGA ≥ 4) who are from countries where etanercept is approved for the treatment of severe pediatric Ps will be randomized to ixekizumab, etanercept, or placebo in a 2:2:1 ratio. 2) Per the main protocol, all other subjects (including those with moderate-to-severe Ps [PASI ≥ 12 and sPGA ≥ 3] from countries where etanercept is not approved for the treatment of severe pediatric Ps, and subjects with moderate pediatric Ps [12 \leq PASI < 20 and sPGA = 3] in countries where etanercept is approved for the treatment of severe pediatric Ps) will be randomized to either ixekizumab or placebo in a 2:1 ratio.
- b At Visit 2, randomization will occur according to the following weight groups: 1) < 25 kg: randomization to ixekizumab 20 mg, receiving a starting dose of 40 mg; 2) 25 kg to 50 kg: randomization to ixekizumab 40 mg, receiving a starting dose of 80 mg; 3) > 50 kg: randomization to 80 mg, receiving a starting dose of 160 mg. A staggered approach to enrollment by weight group will be implemented, with subjects aged > 12 years and weighing > 50 kg enrolling initially to the study. After an initial safety analysis of the first 12 weeks of treatment of 15 subjects weighing > 50 kg, and if no safety concern is identified, subjects will start to enroll in the 25- to 50-kg group. Once data for Week 12 for approximately 15 subjects in the 25- to 50-kg group is gathered, an interim analysis of PK, safety, and efficacy data for all subjects in the study at that point will be performed to confirm doses for future subjects in the study. Once confirmed, all weight groups will be open for enrollment.
- c Subjects receiving ixekizumab 20 mg or 40 mg will receive 1 SC injection of ixekizumab at Week 0 (Visit 2) and 1 SC injection of ixekizumab Q4W at Weeks 4 and 8. Subjects receiving ixekizumab 80 mg will receive 2 SC injections of ixekizumab at Week 0 (Visit 2) and 1 SC injection of ixekizumab Q4W at Weeks 4 and 8.
- d Subjects receiving placebo for ixekizumab 20 mg or 40 mg will receive 1 SC injection of placebo at Week 0 (Visit 2) and 1 SC injection of placebo Q4W at Weeks 4 and 8. Subjects receiving placebo for ixekizumab 80 mg will receive 2 SC injections of placebo at Week 0 (Visit 2) and 1 SC injection of placebo Q4W at Weeks 4 and 8.

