5.3.1. Clinical Protocol RHCD

Subjects who meet all enrollment criteria at Visit 1 and Visit 2 will be randomized in a 2:1 ratio to double-blind treatment with ixekizumab or placebo at Week 0 (Visit 2).

To achieve between-group comparability for region, the randomization will be stratified by region (United States/Canada, European countries, and the rest of the world).

During the Maintenance and Extension periods, all subjects will receive open-label treatment with ixekizumab.

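### The adjusted Period 2 models and SAP 5.3.1 and 6.2 leave out the etanercept-approval/severity stratum used at randomization; the cost is a small loss of efficiency, not bias

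*SAP*

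**What the plan says.** The SAP describes the Week 0 stratification in two ways.

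- **Two factors.** Footnote a to Figure RHCD.5.2 (SAP 5.1), repeated in Attachment 2 of the protocol addendum: "Randomization will be stratified by region (United States/Canada, EU countries, and rest of the world) and by etanercept approval status". Stratum 1 is severe disease (PASI ≥20 or sPGA ≥4) in a country where etanercept is approved; these subjects "will be randomized to ixekizumab, etanercept, or placebo in a 2:2:1 ratio". Stratum 2 is everyone else; they "will be randomized to either ixekizumab or placebo in a 2:1 ratio".
- **One factor.** SAP 5.3.1: "the randomization will be stratified by region (United States/Canada, European countries, and the rest of the world". SAP 6.2: "the randomization at the beginning of the Double-Blind Treatment Period (Period 2) is stratified by geographic region". Both passages are labelled as main-protocol text. SAP 5.3.2, which covers assignment under the addendum, gives the 2:2:1 ratio and names no stratification factor.

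The adjusted models follow the one-factor description. SAP 6.2 says that, outside the primary analysis, "efficacy and health-outcome analyses during Period 2 will include geographic region and baseline weight category in the analysis models". The logistic model in 6.1.3.1, repeated in 6.11.1, has "treatment group, region, baseline sPGA score (severity of Ps), and baseline weight category" as factors. ANCOVA adds the baseline value; MMRM also adds visit and its interactions. No reason is given for leaving out the second factor. For Period 4, by contrast, 6.2 states openly that a stratification factor will not be modelled.

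The co-primary and gated tests are unadjusted Fisher's exact tests (6.5, 6.11.1, 6.11.2).

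**The concern.** An adjusted analysis normally carries the factors by which subjects were randomized. Here one of the two is missing, and the terms already present do not rebuild it. A subject with sPGA 3 and PASI ≥20 in an approved country belongs to the 2:2:1 stratum, although sPGA places that subject with moderate disease. A subject with sPGA 4 in a country without approval is outside the stratum. Membership is severity crossed with country approval, which additive region and sPGA terms cannot reproduce. Addendum section 7.2 also applies 2:2:1 only until about 75 subjects are randomized, so baseline data may not identify the stratum.

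At stake are the logistic regression named as the secondary analysis of both co-primary endpoints, and the ANCOVA and MMRM analyses of the continuous endpoints. A reader of 5.1, 5.3.1 and 6.2 also cannot tell which stratification was used.

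**Working it through.** The plan gives no figure for this point, so there is none to reproduce.

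**1. Is the stratum associated with treatment?** SAP 5.2.2 puts 30 ixekizumab and 15 placebo subjects in stratum 1: 30/15 = 2. SAP 5.2.1 plans 110 and 55 in total. If the 45 are part of the 165, the rest are 80 and 40 (ratio 2); if they are additional, the rest are 110 and 55 (ratio 2). The documents do not say which, but the ratio is the same.

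With no treatment effect and assumed response rates of 30% and 70% in the two strata:
- Ixekizumab: (30 × 0.3 + 80 × 0.7)/110 = 65/110 = 59.1%
- Placebo: (15 × 0.3 + 40 × 0.7)/55 = 32.5/55 = 59.1%

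The difference is 0, so omission does not confound this comparison.

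**2. Linear models (ANCOVA, MMRM).** Let d be the stratum effect, in residual SDs, that the other terms do not capture, and p the share of subjects in the stratum. Omission adds d²p(1−p) to the residual variance, and the standard error ratio is √(1 + d²p(1−p)). The range of d is an assumption.

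| p | d | d²p(1−p) | SE ratio |
|---|---|---|---|
| 45/165 | 0.25 | 0.012 | 1.006 |
| 45/165 | 0.50 | 0.050 | 1.024 |
| 45/210 (if additional) | 0.25 | 0.011 | 1.005 |
| 45/210 (if additional) | 0.50 | 0.042 | 1.021 |

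**3. Logistic model, expected information at the planning rates** (80% and 10%, 110 and 55 subjects, 45/165 in the stratum, no other covariates). Without the term:
- log OR = ln(0.8/0.2) − ln(0.1/0.9) = 1.386 + 2.197 = 3.58
- SE = √(1/(110 × 0.16) + 1/(55 × 0.09)) = √(0.0568 + 0.2020) = 0.509
- z = 7.04

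With the term, holding the overall rates at 80% and 10%:

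| Stratum log OR (assumed) | Treatment log OR | SE | z |
|---|---|---|---|
| −0.5 | 3.62 | 0.514 | 7.04 |
| −1 | 3.71 | 0.526 | 7.06 |
| −2 | 4.07 | 0.569 | 7.14 |

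Adding the term raises both the log odds ratio and its standard error; z hardly moves.

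**4. Logistic model, simulation.** N = 165, permuted 2:1 blocks within region by stratum, with treatment, region and a severity term in the model. Region mix, severity mix and stratum effect are assumed; weight category was not modelled.

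| Stratum log OR | Type I error, without / with (4,000 runs) | Power at treatment log OR 1.0, without / with (2,000 runs) |
|---|---|---|
| 0 | 4.9% / 5.0% | 80.9% / 81.4% |
| −0.5 | 5.9% / 5.9% | not run |
| −1 | 5.2% / 5.5% | 77.7% / 78.5% |
| −2 | 4.0% / 4.4% | 70.4% / 72.2% |

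The Monte Carlo standard error of each type I error figure is about 0.35 points. At stratum log OR −2 the median treatment log OR is 0.97 without the term and 1.04 with it. The 0.5-point power gap at stratum log OR 0 shows that the smaller gaps mean little. At the planning rates power is about 99% either way.

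**The case against.** The strongest reply is that nothing confirmatory is affected. The co-primary and gated tests are unadjusted, and the adjusted models sit outside the testing sequence in 6.5. That stands in full.

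Second, the existing terms already cover part of the stratum. Region is modelled, and SAP 5.1 describes etanercept as a reference arm everywhere except North America, so the United States/Canada level carries some approval status. In the PASI change models the baseline value is baseline PASI, the other half of the severity definition. This also stands: the residual effect may be below the assumed range, and the documents give nothing from which to estimate it.

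Third, 5.3.1 and the 6.2 sentence are labelled main-protocol text, so a cross-reference to the addendum would do there. That is fair, but 5.3.2 does not name the factor either.

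Three stronger readings are tempting, and none is supported.

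- *The adjusted models do not analyse the trial as randomized, so their error rates are unreliable.* Region is in the models, allocation is 2:1 in both strata, and simulated type I error is about the same with and without the term.
- *Standard errors are too wide in every adjusted model.* For the logistic model the direction is the opposite (step 3).
- *The etanercept comparison is confounded.* A comparison pooled over strata would be: with the step 1 rates, 59.1% against 30%, a spurious 29 points. The SAP does not plan it. Its etanercept comparisons use the etanercept-approved ITT population, in which every subject belongs to stratum 1.

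**Conclusion.** The omission and the inconsistency between SAP 5.1 and SAP 5.3.1 and 6.2 are real; the consequence is small. For ANCOVA and MMRM, standard errors are about 0.5% to 2.5% wider than they need be, if a stratum effect of 0.25 to 0.5 SD remains after the other covariates. For the logistic models, the conditional odds ratio is slightly attenuated and power is lower by up to about 2 points, the latter at a strong assumed stratum log OR of −2 and a treatment effect well below the planning one. The ixekizumab-placebo comparison is not biased, type I error is not materially affected, and the primary and gated results do not change. This is a low-priority improvement, worth making because it costs almost nothing.

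**What to change.** 1. In SAP 6.1.3.1 and 6.11.1, add a two-level factor (2:2:1 stratum against all others) to the Period 2 logistic, ANCOVA and MMRM models. Take it from the IWRS record and do not rebuild it from baseline PASI, sPGA and country: the 2:2:1 allocation is capped at about 75 subjects, and Table RHCD.6.12 foresees subjects randomized as severe in error.
2. SAP Version 3 was approved after the primary database lock. Where results are already unblinded, report the model with the added term as a labelled sensitivity analysis beside the planned one.
3. Omit the term where it is constant: in the etanercept-approved ITT population, and in the conditional United States/Canada-only analysis of 6.17 if etanercept is not used there.
4. Reconcile footnote a in 5.1 with 5.3.1, 5.3.2 and 6.2 so that all name the same stratification factors; a cross-reference is enough in the main-protocol sections. If the factor is to stay out of the models, say so in 6.2 with the reason, as is done for Period 4.

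Cost: a few sentences of SAP text and one model term that the IWRS already holds. No change to the design, data collection or primary analysis.

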6.3. Handling of Dropouts or Missing Data

The methods for imputation of missing data to be used in this study are in accordance with the precedent set in other Phase 3 Ps trials (Leonardi et al. 2008; Papp et al. 2008) and ixekizumab Phase 3 pivotal studies (RHAZ, RHBA, and RHBC).

6.3.1. Nonresponder Imputation (NRI)

Analysis of categorical efficacy and health-outcome variables will be assessed using a NRI method. Subjects will be considered nonresponders for the NRI analysis if they do not meet the clinical response criteria or have missing clinical response data at the analysis time point. Randomized patients without at least 1 postbaseline observation will also be defined as nonresponders for the NRI analysis.

6.3.2. Last Observation Carried Forward (LOCF)

An LOCF analysis will be performed on all continuous efficacy and health-outcome variables as a secondary analysis. For patients having missing data at the visit, the last nonmissing postbaseline observation before the missing data will be carried forward to the corresponding

time point for evaluation. Subjects who have a baseline and at least 1 postbaseline observation will be included for evaluation.

6.4. Multicenter Studies

This study will be conducted by multiple investigators at multiple sites internationally. Data from the sites are pooled within geographic region. Unless, otherwise, specified, geographic region will be included in the statistical analysis models. The co-primary endpoints at Week 12 will be summarized by center using descriptive statistics only.

6.5. Multiple Comparisons/Multiplicity

A multiple testing strategy for the primary and major secondary objectives will be implemented to control the family-wise type I error rate at a 2-sided α level of 0.05. The primary and key secondary comparisons will be tested by using the primary analysis method, Fisher's exact test, with an NRI missing-data imputation approach.

A gatekeeping approach will be used for multiple comparisons to control the family-wise error rate. To assess whether ixekizumab Q4W is superior to placebo, the following endpoints will be tested:

- Primary 1: Proportion of subjects achieving PASI 75 at Week 12
- Primary 2: Proportion of subjects achieving sPGA (0,1) at Week 12
- Secondary 1: Proportion of subjects achieving PASI 90 at Week 12
- Secondary 2: Proportion of subjects achieving sPGA (0) at Week 12
- Secondary 3: Proportion of subjects achieving PASI 100 at Week 12
- Secondary 4: Proportion of subjects achieving ≥ 4 point improvement for subjects who had a baseline Itch numeric rating scale (NRS) ≥ 4 at Week 12
- Secondary 5: Proportion of subjects achieving PASI 75 at Week 4
- Secondary 6: Proportion of subjects achieving sPGA (0,1) at Week 4

The Primary 1 will first be tested at 2-sided $\alpha=0.05$. If successful, the test for Primary 2 will be performed at 2-sided $\alpha=0.05$. Otherwise, the test will stop. If the Primary 2 endpoint is successful, the Secondary 1 endpoint will be tested. The test will continue to the last endpoint if all the prior tests are successful. If a test is not successful, all subsequent tests will not be tested.

6.6. Use of an "Efficacy Subset" of Patients

The PPS is defined above in Section 6.1.1 and is an efficacy subset of patients. The analysis of the co-primary endpoints will be repeated using the PPS.

6.7. Patient Disposition

Patient flow will be summarized from entered to randomized to completion, and analysis populations will be listed and summarized by treatment group.

Patient disposition from study will be listed and summarized with reasons for disposition for the ITT Population and the Follow-Up Population, respectively.

Patient disposition from study treatment will be listed and summarized for the ITT Population for the Double-Blind Treatment Period (Period 2) and the ITT Population of etanercept approved countries for the Double-Blind Treatment Period (Period 2) in Protocol Addendum RHCD(2) with reasons for disposition, which will be compared between and among treatment groups using Fisher's exact test.

Time to study treatment discontinuation due to any reason (in weeks) will be summarized by treatment group and graphically presented using Kaplan-Meier technique. The log-rank test will be used to compare time to study treatment discontinuation between treatment groups. Time to study treatment discontinuation will be calculated as:

$$\frac{\text{Date of study treatment discontinuation} - \text{Date of first dose} + 1}{7}$$

If the date of first dose is missing, the date of randomization will be used. Patients completing the study treatment will be censored at the date of completion.

Patient allocation by region, country, and center/site will be summarized with number of patients who entered the study, number of ITT patients for each dosing regimen, number of patients discontinued from study treatment, and number of patients discontinued from study.

6.8. Patient Characteristics

6.8.1. Demographics and Baseline Characteristics

Patient demographic variables and baseline characteristics will be summarized by treatment group and, overall, for the ITT Population and the ITT Population – etanercept-approved countries and the Double-Blind, Randomized Withdrawal Period Population. The continuous variables will be summarized using descriptive statistics, and the categorical variables will be summarized using frequency counts and percentages. The comparisons between treatment groups will be conducted using the Fisher's exact test for categorical data, and an analysis of variance model with treatment group as a factor for continuous data.

The following demographic variables and baseline characteristics will be summarized:

- Age (years)
- Age category: <12 years; and ≥12 years
- Gender
- Ethnicity
- Race
- Weight (kg): measured at Visit 2
- Weight Category: <25 kg; ≥25 to ≤50 kg; and >50 kg
- Height (cm): measured at Visit 1
- Body mass index (BMI) (kg/m²): BMI will be calculated as:

$$BMI (kg/m^2) = \frac{Weight(kg)}{(Height(m))^2}$$

- Habits (only for subjects ≥12 years old)

- Caffeine consumption: never; current; former
- Alcohol consumption: never; current; former
- Tobacco consumption: never; current; former
- Country: Argentina, Canada, Czech Republic, France, Germany, Hungary, Mexico, Netherlands, Poland, Russia, Spain, United States
- Geographic region:
 - United States/Canada (United States, Canada)
 - European Union (Czech Republic, France, Germany, Hungary, Netherlands, Poland, Spain)
 - Rest of the world (Argentina, Mexico, Russia)
- Geographic region:
 - United States/Canada (United States, Canada)
 - Other
- Previous systemic therapy: never used; nonbiologic only; biologic only; biologic and nonbiologic.
 - Nonbiologics are defined as: methotrexate; cyclosporine; corticosteroids; acitretin; fumaric-acid derivatives; apremilast; or other nonbiologics
 - Biologics are defined as: efalizumab; ustekinumab; infliximab; etanercept; alefacept; adalimumab; golimumab; certolizumab pegol; secukinumab; or other biologics
- Tuberculosis (TB) exposure: positive; negative
- Age at Ps onset (in years)
- Duration of Ps (in years): will be calculated using the date of Ps onset (as recorded on the Prespecified Medical History - Psoriasis electronic case report form [eCRF] page) as follows:

$$\begin{aligned}
 & \textit{Duration of psoriasis (years)} \\
 & = \frac{\textit{Date of informed consent} - \textit{Date of psoriasis onset}}{365.25}
 \end{aligned}$$

- Age at psoriasis diagnosis (in years)
- Duration of psoriasis diagnosis (in years): will be calculated using the date of psoriasis diagnosis (as recorded on the Prespecified Medical History – Psoriasis eCRF page) as follows:

$$\begin{aligned}
 & \textit{Duration of psoriasis diagnosis (years)} \\
 & = \frac{\textit{Date of Visit 2} - \textit{Date of psoriasis diagnosis}}{365.25}
 \end{aligned}$$

- Baseline sPGA
- Baseline sPGA category: 3; 4; and 5
- Baseline sPGA category: 3; and combined 4 or 5
- Baseline PASI score
- Baseline PASI category: <20; and ≥20
- Baseline BSA (%)
- Baseline BSA category: <20%; and ≥20%
- Nail psoriasis: yes; and no

- Baseline Nail Psoriasis Severity Index (NAPSI) score
- Scalp psoriasis: yes; and no
- Baseline Psoriasis Severity Index (PSSI) score
- Palmoplantar psoriasis: yes; and no
- Baseline Palmoplantar Psoriasis Severity Index (PPASI) score
- Baseline Itch NRS score
- Baseline Itch NRS category: <4 ; and ≥ 4
- Baseline Children's Dermatology Life Quality Index (CDLQI) total score
- Baseline Dermatology Life Quality Index (DLQI) total score
- Patient's Global Assessment of Disease Severity (PatGA)
- PatGA category: 0; 1; 2; 3; 4; and 5
- Baseline Children's Depression Rating Scale, Revised (CDRS-R)
- Baseline CDRS-R category: ≤ 28 ; 29-39; and ≥ 40
- Baseline Columbia Suicide Severity Rating Scale (C-SSRS)
- Binary questions on psoriasis location
- Tanner Stage Scale

By-patient listings of demographic and baseline characteristics, respectively, for the ITT Population will be provided.

